10.8 Patient Reported Outcomes

The following instruments will be used to collect patient reported outcomes (PROs): EuroQol 5 Dimensions 5 Levels Health State Instrument (EQ-5D-5L) and Fatigue Severity Scale (FSS). Missing data for each measurement will be handled as described in Section 6.3.

The following exploratory analyses of PROs will be performed:

- mean change from baseline in EQ-5D-5L health index score and its VAS score to each applicable post-baseline time point;
- mean change from baseline in the FSS score and its VAFS score to each applicable post-baseline time point.

Subject's responses to the EQ-5D-5L will be combined into a unique health state using a 5-digit code with 1 digit from each of the 5 dimensions. The EQ-5D-5L states will be converted into a single preference-weighted health utility index score by applying country-specific weights (if available) or US weights (if not available). The VAS score will be measured separately.

The FSS measures the impact of fatigue over the past week on specific types of functioning. The survey consists of 9 questions using a 7-point Likert scale. A total score

is calculated as the average of the individual item responses (adding up all the answers and dividing by nine). Subjects also rate their perception of their fatigue on a separate visual analogue fatigue scale (VAFS). Higher FSS scores indicate a higher degree of impact of fatigue.

Summary statistics (n, mean, SD, median, minimum and maximum) for the mean change from baseline to each applicable visit will be provided for the EQ-5D-5L index and its VAS scores, the FSS score and its VAFS scores.

11.0 Safety Analysis

11.1 General Considerations

All subjects who receive at least one dose of study drug will be included in the safety analyses. Safety data will be summarized for each treatment arm using the safety population.

11.2 Analysis of Adverse Events

11.2.1 Treatment-Emergent Adverse Events

Adverse events will be coded using the Medical Dictionary for Regulatory Activities (MedDRA). Treatment-emergent adverse events are defined as any event that begins or worsens in severity after initiation of study drug through 30 days after the last dose of study drug. Events where the onset date is the same as the study drug start date are assumed to be treatment-emergent. If an incomplete onset date was collected for an adverse event, the event will be assumed to be treatment-emergent, unless there is other evidence that confirms that the event was not treatment-emergent (e.g., the event end date was prior to the study drug start date).

11.2.1.1 Tabulations of Treatment-Emergent Adverse Events

Adverse event data will be summarized and presented using primary MedDRA system organ classes (SOCs) and preferred terms (PTs) by treatment arm according to the version of the MedDRA coding dictionary used for the study at the time of database lock. The

actual version of the MedDRA coding dictionary used will be noted in the clinical study report. The system organ classes will be presented in alphabetical order and the preferred terms will be presented in alphabetical order within each system organ class.

Adverse Event Overview

An overview of adverse events will be presented consisting of the number and percentage of subjects experiencing at least one event for the following adverse event categories:

- Any treatment-emergent adverse event;
- Treatment-emergent adverse events with a "reasonable possibility" of being related to DAAs (Ombitasvir/ABT-450/r);
- Treatment-emergent adverse events with a "reasonable possibility" of being related to RBV (applicable for RBV-containing arms);
- Severe treatment-emergent adverse events;
- Serious treatment-emergent adverse events;
- Treatment-emergent adverse events leading to discontinuation of study drug;
- Treatment-emergent adverse events leading to interruption of study drug;
- Treatment-emergent adverse events leading to RBV dose modification (applicable for RBV-containing arms);
- Treatment-emergent adverse events leading to death;
- Deaths.

The adverse event overview summary will be provided for each treatment arm.

Adverse Event by SOC and PT

The following summaries of adverse events will be generated by treatment arm:

- Treatment-emergent adverse events;
- Treatment-emergent adverse events with a "reasonable possibility" of being related to DAAs (Ombitasvir/ABT-450/r);

- Treatment-emergent adverse events with a "reasonable possibility" of being related to RBV;
- Serious treatment-emergent adverse events;
- Moderate or severe treatment-emergent adverse events;
- Severe treatment-emergent adverse events;
- Grade 3 or 4 (see definition below) treatment-emergent adverse events;
- Treatment-emergent adverse events leading to discontinuation of study drug;
- Treatment-emergent adverse events leading to interruption of study drug;
Treatment-emergent adverse events leading to RBV dose modification;
- Treatment-emergent adverse events leading to death;
- Treatment-emergent adverse events leading to concomitant medication use
(events with other action taken of "concomitant medication prescribed").

For all adverse event summaries, the number and percentage of subjects experiencing treatment-emergent adverse events will be tabulated according to SOC and PT. Subjects reporting more than one adverse event for a given PT will be counted only once for that term (most severe incident for the severity tables and most related incident for the relationship tables). Subjects reporting more than one adverse event within a SOC will be counted only once for that SOC. Subjects reporting more than one adverse event will be counted only once in the overall total.

A listing of treatment-emergent adverse events grouped by body system and preferred term with subject numbers will be created for each treatment arm.

Adverse Event by PT

The number and percentage of subject experiencing treatment-emergent adverse events will be tabulated according to preferred term and sorted by overall frequency for the total number of subjects in each treatment arm. Similar summaries will be provided for moderate to severe treatment-emergent adverse events and treatment-emergent adverse events with a "reasonable possibility" of being related to DAAs. These summaries will display for each treatment group and be sorted by overall total.

Adverse Event of Special Interest

Specific treatment-emergent adverse events of special interest, which may be searched using Standardized or Company MedDRA Queries, will be summarized and include severe cutaneous reactions and anemia. The search criteria for the adverse event of interest are as follows:

- Severe Cutaneous Reactions
SMQ "Severe cutaneous adverse reactions" (narrow search)
- Anemia
SMQ "Haematopoietic erythropenia" (broad search) plus the following preferred terms:
Haemolytic anaemia,
Coombs negative haemolytic anaemia,
Coombs positive haemolytic anaemia.

For each adverse event of interest (severe cutaneous reactions and anemia), the number and percentage of subjects experiencing at least one treatment-emergent adverse event in the search for the event of interest will be presented for each treatment arm and overall and by SOC and PT.

A listing of treatment-emergent adverse events for subjects meeting the search criterion will be provided for the adverse event of special interest.

Adverse Event by Maximum Severity

Treatment-emergent adverse events and treatment-emergent adverse events with a "reasonable possibility" of being related to DAAs will be summarized by maximum severity of each preferred term. If a subject has an adverse event with unknown severity, then the subject will be counted in the severity category of "unknown," even if the subject has another occurrence of the same event with a severity present. The only exception is if the subject has another occurrence of the same adverse event with the most extreme severity – "Severe." In this case, the subject will be counted under the "Severe" category.

Adverse Events by Maximum Severity Grade Level

Treatment-emergent adverse events will be summarized by maximum severity grade level of each preferred term. Each preferred term will be assigned to a grade level based on severity and seriousness, adapted from the Division of AIDS (DAIDS) table for grading severity of adverse events. All serious adverse events will be categorized as Grade 4. Nonserious adverse events categorized by the investigators as mild, moderate, or severe will be categorized as Grade 1, Grade 2, or Grade 3, respectively. If a subject has a nonserious adverse event with unknown severity, then the subject will be counted in the severity grade level category of "unknown," even if the subject has another occurrence of the same event with a severity present. The only exception is if the subject has another occurrence of the same adverse event with the most extreme severity – "Severe." In this case, the subject will be counted under the "Grade 3" category. Similarly, if a subject has an adverse event with unknown seriousness, then the subject will be counted in the severity grade level category of "unknown" unless the subject has another occurrence of the same adverse event that is marked serious. In this case, the subject will be counted under the "Grade 4" category.

Adverse Event by Maximum Relationship

Treatment-emergent adverse events also will be summarized by maximum relationship of each preferred term to study drug (DAA), as assessed by the investigator. If a subject has an adverse event with unknown relationship, then the subject will be counted in the relationship category of "unknown," even if the subject has another occurrence of the same event with a relationship present. The only exception is if the subject has another occurrence of the same adverse event with a relationship assessment of "Reasonable Possibility." In this case, the subject will be counted under the "Reasonable Possibility" category.

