6.3 Relationship to Study Drug

The investigator will use the following definitions to assess the relationship of the adverse event to the use of study drug. Assessment of relatedness will be made with respect to the DAAs (ombitasvir/ABT-450/r and SOF) and with respect to RBV:

Reasonable Possibility	An adverse event where there is evidence to suggest a causal relationship between the study drug and the adverse event.
No Reasonable Possibility	An adverse event where there is no evidence to suggest a causal relationship between the study drug and the adverse event.

For causality assessments, events assessed as having a reasonable possibility of being related to the study drug will be considered "associated." Events assessed as having no reasonable possibility of being related to study drug will be considered "not associated." In addition, when the investigator has not reported a causality or deemed it not assessable, AbbVie will consider the event associated.

If an investigator's opinion of no reasonable possibility of being related to study drug is given, an "Other" cause of event must be provided by the investigator for the SAE.

[figure not shown]
6.4

Adverse Event Collection Period

All serious adverse events as well as protocol-related nonserious adverse events will be collected from the time the subject signed the study-specific informed consent until study drug administration. From the time of study drug administration until 30 days following discontinuation of study treatment has elapsed, all adverse events and serious adverse events will be collected, whether solicited or spontaneously reported by the subject. In addition, serious adverse events will be collected from the time the subject signed the study-specific informed consent until 30 days after the last dose of study drug.

Adverse event information will be collected as shown in [Figure 2](#).

Figure 2. Adverse Event Collection

6.5

Adverse Event Reporting

In the event of a SAE, whether associated with study drug or not, the Investigator will notify Clinical Pharmacovigilance within 24 hours of the site being made aware of the SAE by entering the SAE data into the electronic data capture (EDC) system. SAEs that occur prior to the site having access to the RAVE® system or if RAVE is not operable should be faxed to Clinical Pharmacovigilance within 24 hours of being made aware of the SAE.

Ombitasvir/ABT-450/Ritonavir
M14-567 Protocol
EudraCT 2014-003147-35

FAX to: [REDACTED]

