4.0 Study Objectives, Design and Procedures

4.1 Objectives

The primary objectives of this study are to assess the safety and efficacy (the percentage of subjects achieving a 12-week sustained virologic response, SVR₁₂ [HCV ribonucleic acid {RNA} < lower limit of quantification {LLOQ} 12 weeks following treatment]) of co-formulated ombitasvir with ABT-450/r (ombitasvir/ABT-450/r) co-administered with sofosbuvir (SOF) with or without ribavirin (RBV) for 12 weeks in HCV genotype 3-infected adult subjects with and without cirrhosis, and 8 and 6 weeks in HCV genotype 2-infected adult subjects without cirrhosis.

The secondary objectives of this study are to assess the percentage of subjects with on treatment virologic failure and the percentage of subjects with relapse post-treatment (PT), and characterize the pharmacokinetics of direct-acting antiviral agents (DAAs)

including ombitasvir/ABT-450/r, SOF, GS-331007 (predominant circulating metabolite of SOF), and RBV (if applicable).

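### SAP 11.2.1.1 leaves sofosbuvir out of its DAA-related adverse-event category and does not carry through the protocol's rule for missing causality

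*SAP*

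**What the plan says.** **Which drugs.** Protocol 6.3: "Assessment of relatedness will be made with respect to the DAAs (ombitasvir/ABT-450/r and SOF) and with respect to RBV". There are two assessments, one for the DAAs jointly and one for ribavirin (RBV). SAP 11.2.1.1 names the DAA-related category in its overview list and again in its SOC/PT list. Both times the phrase is "of being related to DAAs (Ombitasvir/ABT-450/r"), without SOF. SAP 4.1 describes the DAAs as "including ombitasvir/ABT-450/r, SOF, GS-331007 (predominant circulating metabolite of SOF), and RBV (if applicable").

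**Missing causality.** Protocol 6.3: "when the investigator has not reported a causality or deemed it not assessable, AbbVie will consider the event associated". The SAP's maximum-relationship summary says: "If a subject has an adverse event with unknown relationship, then the subject will be counted in the relationship category of" unknown. The one exception is a subject with another occurrence of the same event rated a reasonable possibility. That summary reports "maximum relationship of each preferred term to study drug (DAA), as assessed by the investigator". The overview, SOC/PT, by-PT and maximum-severity tables say nothing about missing causality.

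**Declared departures.** SAP 12.1 lists only the resistance analyses as changed relative to the protocol.

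**The concern.** Safety is a primary objective, and protocol 3.1 describes this as the first study of the combination in genotype 3 patients. Every arm receives SOF. The tables of drug-related events are where the report says which drugs an event was attributed to.

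Two things are at stake. The first is whether the row label names the drugs that the investigator was asked about. The second is whether an event without a usable causality rating counts as related, which is how the protocol says the sponsor will regard it. The SAP's wording differs from protocol 6.3 on the first and does not carry its rule through on the second. Because SAP 12.1 mentions neither, a programmer has no sign that a change was intended.

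**Working it through.** The plan gives no figure for this point, so there is none to reproduce. The check compares the texts and then sizes one reclassified subject.

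**Step 1. What counts as a DAA.**

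| Place | Drugs named |
|---|---|
| Protocol 5.5.1 (DAA study drugs) | ombitasvir/ABT-450/r and SOF |
| Protocol 6.3 (relatedness) | ombitasvir/ABT-450/r and SOF jointly; RBV separately |
| SAP 4.1 (objectives) | list includes SOF |
| SAP 7.3 (first dose of study drug) | ombitasvir/ABT-450/r or SOF |
| SAP 11.2.1.1, overview and SOC/PT rows | ombitasvir/ABT-450/r only |
| SAP 11.2.1.1, by-PT, maximum-severity and maximum-relationship tables | DAA, not spelled out |

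The SAP 4.1 list is loose, since it also contains a metabolite and RBV. It still places SOF with the DAAs, and the two parentheses in 11.2.1.1 are the only text in the table above that leaves it out.

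**Step 2. What the omission does.** It depends on how causality is captured.

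- One joint DAA item, as protocol 6.3 describes: an event attributed to SOF is recorded as DAA-related and enters the row. The count is right, and the label wrongly points to ombitasvir/ABT-450/r alone.
- SOF captured separately, or dropped in programming to match the label: an event judged related only to SOF enters no DAA row. Arms A and F have no RBV (10 + 10 = 20 subjects), so it would enter no drug-related row there at all.

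**Step 3. Missing causality, table by table.**

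| Table | Rule in the SAP | Protocol 6.3 |
|---|---|---|
| Maximum relationship | unknown, unless another occurrence is a reasonable possibility | associated |
| Overview, SOC/PT, by-PT and maximum severity (related events) | none stated | associated |

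The first row is a stated difference and the second is a gap. If only events actually rated as a reasonable possibility are counted, any error is an undercount.

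**Step 4. Size.** Planned arms from SAP 4.2 are A 10, B 10, C 10, D 10, E 20 and F 10, total 70. Moving one subject changes the related percentage by 1/n:

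- n = 10: 1/10 = 10.0 points
- n = 20: 1/20 = 5.0 points
- n = 70: 1/70 = 1.4 points

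In the overview row these are upper limits, because a subject who already has another related event does not move.

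The documents give no rate of missing causality. Assuming a per-subject rate m, the chance that at least one of n subjects is affected is 1 − (1 − m)^n:

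| m (assumed) | n = 10 | n = 20 | n = 70 |
|---|---|---|---|
| 0 | 0 | 0 | 0 |
| 0.01 | 0.10 | 0.18 | 0.51 |
| 0.02 | 0.18 | 0.33 | 0.76 |
| 0.05 | 0.40 | 0.64 | 0.97 |
| 0.10 | 0.65 | 0.88 | >0.99 |

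**The case against.** A reader might infer that the drug-related counts will be wrong. The documents do not show that. Protocol 6.3 describes one joint DAA judgement and no SOF-only item, so on its face the fault is an incomplete label over a correct count. The loss in Arms A and F needs a separate SOF item or a programming choice, and the eCRF is not supplied. All treatment-emergent events are also tabulated regardless of causality, so no event leaves the safety summary. This objection stands against the stronger reading. It does not rescue the label.

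A reader might also infer that events without a rating drop out of every reasonable-possibility count. The unknown rule is written for one table, which reports the investigator's own assessment. Showing a missing rating as unknown there is accurate and visible. The other tables are silent, not contrary. Protocol 6.3 states how the sponsor will regard such events, and the tabulation text in protocol 8.1.5.1 gives no rule for them. So this part is weaker than the first. Even so, 6.3 is the protocol's definition of what counts as associated, and the SAP should say whether its counts follow it.

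A further objection is that protocol 8.1 and SAP 6.3 allow no imputation in safety analyses. That stands as a drafting point: the remedy has to be reconciled with that sentence. It is not a bar, because SAP 11.2.1 already assumes that events with incomplete onset dates are treatment-emergent.

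Finally, the supplied protocol covers Arms A and B and about 20 subjects, while the SAP covers Arms A to F and about 70. The SAP therefore follows a later protocol version whose section 6.3 could not be checked. This limits every comparison with the protocol. It does not touch the SAP's disagreement with itself about SOF.

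**Conclusion.** The SAP's definition of its DAA-related category is wrong as written. It omits a drug that protocol 6.3 and SAP 4.1 both include, and no departure is declared. The likely result is a mislabelled attribution. Omission of SOF-related events is possible only if the eCRF or the programming separates SOF.

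On missing causality, the SAP differs from protocol 6.3 in one table and gives no rule in the others. Related-event counts could be understated relative to the protocol's rule, by up to 10 points per subject in an arm of 10, 5 points in an arm of 20 and 1.4 points over 70. The number of such subjects is unknown and may be 0.

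Both conclusions about the protocol assume that section 6.3 of the governing version reads as in the one supplied. No efficacy result is affected.

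**What to change.** In SAP 11.2.1.1:

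1. Change the parenthesis in the overview row and in the SOC/PT row to name ombitasvir/ABT-450/r and SOF.
2. State once that DAAs has this meaning throughout the section, so that the by-PT, maximum-severity and maximum-relationship tables inherit it.
3. In all reasonable-possibility counts, treat missing or not-assessable causality as associated, citing protocol 6.3, and footnote the number so assigned.
4. Say that this is a protocol-defined classification and an exception to the no-imputation statement in SAP 6.3.
5. The maximum-relationship table may keep showing the investigator's missing rating as unknown.

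Before finalising, confirm the causality items on the eCRF and section 6.3 of the governing protocol version.

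The cost is a few lines of SAP text and table footnotes, with no new data. Related counts may come out slightly higher.

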8.1.5.1 Adverse Events

Adverse events will be coded using the Medical Dictionary for Regulatory Activities (MedDRA).²⁴ The number and percentage of subjects with treatment-emergent adverse events (i.e., any event that begins or worsens in severity after initiation of study drug through 30 days post-study drug dosing) will be tabulated by primary MedDRA System Organ Class (SOC) and preferred term (PT) for each treatment arm and overall. The tabulation of the number of subjects with treatment-emergent adverse events by severity rating and relationship to study drug will also be provided. Subjects reporting more than one adverse event for a given MedDRA preferred term will be counted only once for that term using the most severe incident for the severity rating table and the most related for the relationship to study drug table. Subjects reporting more than one type of event within a SOC will be counted only once for that SOC.

Additional analyses will be performed if useful and appropriate.

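### In the maximum severity grade table, the unknown-severity rule can count a subject with a serious adverse event as unknown or Grade 3 instead of Grade 4

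*SAP*

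**What the plan says.** The text is in SAP section 11.2.1.1, under the label for adverse events by maximum severity grade level. It grades events from seriousness and investigator-rated severity, then adds two subject-level rules for missing ratings.

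- **Serious events:** "All serious adverse events will be categorized as Grade 4".
- **Nonserious events:** "Nonserious adverse events categorized by the investigators as mild, moderate, or severe will be categorized as Grade 1, Grade 2, or Grade 3, respectively".
- **Unknown severity:** "If a subject has a nonserious adverse event with unknown severity, then the subject will be counted in the severity grade level category of" (the category named is unknown). This applies even when another occurrence of that event has a rating. "The only exception is if the subject has another occurrence of the same adverse event with the most extreme severity", meaning Severe, and that subject is placed in Grade 3.
- **Unknown seriousness:** the subject is counted as unknown unless another occurrence of the same event is marked serious, in which case the subject is placed in Grade 4.

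The same section has matching rules for the plain severity table (unknown gives way only to Severe) and the relationship table (unknown gives way only to Reasonable Possibility). It also lists a by-term table of Grade 3 or 4 events, which points to the grade definition.

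**The concern.** A maximum-grade table should place each subject at the worst grade observed for the term. The SAP makes seriousness sufficient for Grade 4, but the unknown-severity rule never looks at seriousness. Its exception uses the wording of the plain severity table, where Severe is the top category. On the grade scale Severe is only Grade 3, and there is a level above it. The plain severity, relationship and unknown-seriousness rules all protect the top category of their scale. This rule stops one level short.

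If it is programmed as written, a subject can appear in the serious-event table for a preferred term and, for the same term, as unknown or Grade 3 in the maximum-grade table. Safety is part of the primary objective and the arms are small, so a single misplaced subject is visible in a table row.

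**Working it through.** The plan gives no figure to reproduce. The check applies the sentences literally to every combination of occurrences within one preferred term.

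**Inputs (SAP 11.2.1.1).** Seriousness can be no, yes or unknown. Severity can be mild, moderate, severe or unknown. That gives 3 × 4 = 12 event types and 12 × 11 / 2 = 66 pairs of different types. Each literal result was compared with the highest known grade in the pair.

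**Step 1: nonserious unrated event plus a serious event of the same term.**

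| Serious event's severity | Unknown-severity rule gives | Serious-event sentence requires |
|---|---|---|
| Mild | Unknown | Grade 4 |
| Moderate | Unknown | Grade 4 |
| Unrated | Unknown | Grade 4 |
| Severe | Grade 3 | Grade 4 |

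All 4 of 4 pairs miss Grade 4. The unknown-seriousness rule does not help, because neither event has unknown seriousness.

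**Step 2: nonserious unrated event plus a severe event of unknown seriousness.** The unknown-severity rule finds a Severe occurrence and gives Grade 3. The unknown-seriousness rule finds no serious occurrence and gives unknown. Both rules apply and neither is given priority.

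**Step 3: three different event types, including a nonserious unrated event and at least one serious event.** There are 34 such triples (55 − 21, that is, C(11,2) − C(7,2)).

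- In 18 the only answer is wrong: 9 give unknown and 9 give Grade 3.
- In the other 16 an event of unknown seriousness is also present, so the second rule gives Grade 4 while the first gives unknown (9) or Grade 3 (7).
- None of the 34 gives Grade 4 as its only answer.

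**Step 4: all pairs.** In 19 of 66 pairs a literal result differs from the highest known grade. They are not all faults:

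- 4 are the missed Grade 4 cases in step 1.
- 1 is the two-answer case in step 2.
- 10 have unknown displacing Grade 1 or Grade 2.
- 4 have an event of unknown seriousness displacing a nonserious severe event (Grade 3).

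The last two groups (14 pairs) follow from a convention for missing ratings, discussed under the objection. The faults are the first 5.

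**Step 5: size per subject.** SAP section 4.2 plans about 10 subjects in each of Arms A, B, C, D and F, and about 20 in Arm E. One misplaced subject is 1/10 = 10 percentage points or 1/20 = 5 percentage points of an arm. This is the weight of one case, not an estimate of how often it happens.

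**Step 6: after the fix.** With any serious occurrence giving Grade 4 first, all four pairs in step 1 and all 34 triples in step 3 give Grade 4.

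**The case against.** **A charitable reading exists.** The unknown-severity rule may have been meant to compare nonserious occurrences only, with the serious-event sentence settling everything else. That is plausible as intent. But the exception refers to another occurrence of the same event without restricting it to nonserious ones, and it is described as the only exception. A programmer following the text would not reach Grade 4.

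**The trigger is remote.** Protocol section 6.0 has the investigator record severity for every adverse event, section 6.2 defines the ratings, and SAP section 4.4.1 has data cleaned before each lock. The fault needs a severity still missing at lock and a serious occurrence of the same term in the same subject. Serious events also have their own overview row and by-term table, and SAP section 11.2.2 lists them. This stands: no serious event disappears from the report.

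**Four stronger readings are tempting, and the documents do not support them.**

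- *The SAP conflicts with the protocol.* Protocol section 8.1.5.1 counts a subject once per term, "using the most severe incident for the severity rating table". It does not say how an unrated incident ranks, and it has no table combining severity with seriousness. The SAP repeats the most-severe principle and adds a missing-rating convention, and Protocol section 8.1 leaves detailed methods to the SAP.
- *Ranking unknown above moderate is an error.* An unrated event may have been severe, so the maximum for moderate plus unrated is genuinely not known. Using the highest known grade instead could itself understate severity.
- *Counting nonserious severe plus unknown seriousness as unknown is an error.* The maximum is either Grade 3 or Grade 4 and cannot be determined, so unknown is defensible as a label.
- *The Grade 3 or 4 table understates serious and severe events.* The SAP does not say that table is built from the subject-level maximum. If it uses event-level grades, a serious event stays in it. Even on the subject-level assumption, the serious severe case becomes Grade 3 and remains.

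**Conclusion.** The point holds as an internal contradiction in SAP section 11.2.1.1. As written, a subject with a nonserious unrated occurrence and a serious occurrence of the same term is counted as unknown or Grade 3, although the SAP grades every serious event 4 and the table is meant to show the maximum. The two-answer case is a smaller gap of the same kind: precedence between the two unknown rules is not stated.

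The conclusion rests on a literal reading of the exception. The effect is confined to the maximum-grade table, unless the Grade 3 or 4 table is derived from the subject-level grade. In that event, subjects counted as unknown would drop out of it too. Few or no subjects are likely to be affected, and efficacy is untouched. This is a minor correction, worth making because the stated rule gives a wrong maximum grade and the repair is simple.

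**What to change.** Amend the grade-level paragraph of SAP section 11.2.1.1 as follows.

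1. State that any serious occurrence of the preferred term places the subject in Grade 4, and that this takes precedence over both the unknown-severity and the unknown-seriousness rules.
2. Give one rank order for the remaining cases, for example Grade 4 > Grade 3 > unknown > Grade 2 > Grade 1. That order keeps unknown above moderate. It would move nonserious severe plus unknown seriousness from unknown to Grade 3, so the sponsor should choose it deliberately.
3. State how a severe event of unknown seriousness is graded on its own. Without this, the rank order does not settle the two-answer case.
4. State whether the Grade 3 or 4 table uses event-level grades or the subject-level maximum.

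The cost is a few sentences in the SAP and the matching program logic. No data collection changes, and no protocol amendment is needed.
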